8.4.1 Laboratory evaluations

A central laboratory will be used for analysis of all specimens collected. Details on the collections, shipment of samples and reporting of results by the central laboratory are provided to investigators in the laboratory manual. All patients with laboratory tests containing clinically significant abnormalities should be followed regularly until the values return to within the normal ranges or until a valid reason other than drug-related adverse experiences is identified, even after the medication has discontinued.

Safety Laboratory assessments (hematology and clinical chemistry) will be performed at Screening and at 6 hour post QMF149 dose on Day 6.

Clinically notable laboratory findings are defined in Section 16.1.

Clinically significant abnormalities must be recorded as either medical history/current medical conditions or adverse events as appropriate.

Test Category	Test Name
Hematology	Hemoglobin, hematocrit, red blood cell count, white blood cell count with differential, and
	platelet count will be measured.
	Peripheral blood eosinophil counts will be captured with a unit of cells/ mcL.

Table 8-3Laboratory evaluations

Test Category	Test Name
Chemistry	Albumin, alkaline phosphatase, aspartate aminotransferase (AST) or Serum Glutamic Oxaloacetic Transaminase (SGOT), alanine aminotransferase (ALT) or Serum Glutamic Pyruvic Transaminase (SGPT), bilirubin, creatinine, γ-GT, glucose, sodium, potassium, magnesium, BUN and uric acid will be measured.
	If the total bilirubin concentration is increased above 1.5 times the upper limit of normal range, total bilirubin should be differentiated into the direct and indirect reacting bilirubin.
Urinalysis	Dipstick measurements for specific gravity, pH, protein, glucose and blood will be performed at Screening and Day 6. If the urine dipstick is abnormal, the sample will be sent to central laboratory for additional testing, including assessment of WBC and RBC sediments.
	Macroscopic Panel (Color, Bilirubin, Blood, Glucose, Ketones, Leukocytes esterase, Nitrite, pH, Protein, Specific Gravity, Urobilinogen)
Pregnancy Test	Serum / Urine pregnancy test (refer to Section 8.4.3)

8.4.2 Electrocardiogram (ECG)

ECGs must be recorded after the patient rests (10 minutes if possible) in the supine position to ensure a stable baseline. When the ECG recording time coincides with vital signs, and blood draws, the ECG should be performed first, followed by vital signs and the blood draws.

Centralized ECG

At screening an ECG will be measured to test for eligibility for trial inclusion. Patients with an abnormal ECG at screening, due to technical/mechanical faults, may be rescreened.

ECG will be measured at Screening and on Day 6 at pre-dose and 20-min- post-dose of study medication as indicated in Section 16.4. ECGs should include 12 standard leads. ECG will be sent electronically for central review directly from the ECG machine. One print-out will be generated and kept at the investigator site as source documentation will be dated and signed. The patient's number, the date, actual time of the tracing, and Study Code must appear on each page of the tracing.

Full details of all procedures relating to the ECG collection and reporting will be contained in an investigator manual to be provided by the central ECG group to each investigator site.

In the event that the central cardiologist reports that an ECG is abnormal, the investigator must assess whether the ECG abnormality is clinically significant or not. A clinically significant abnormality should be reported as an AE. If necessary a pediatric cardiologist may be consulted. Clinically significant ECG findings at baseline must be discussed with the sponsor before administration with investigational treatment. If a patient experiences a clinically significant change in cardiac rhythm or other clinically significant cardiovascular abnormality, the investigator should consider withdrawing the patient from the study. Clinically significant abnormalities should be recorded on the relevant section of the medical history/Current medical conditions/AE CRF page as appropriate.

8.4.3 Pregnancy and assessments of fertility

Females of child-bearing potential are defined as all females physiologically capable of becoming pregnant. This includes female pediatric patients who are menarchal or who become menarchal during the study and may participate in this study.

Serum pregnancy test will be performed for all females of child-bearing potential according to the protocol assessment schedule (Table 8-1).

All menarchal girls and their parents/caregivers should be informed about the potential risks of pregnancy and the need to prevent pregnancy during the study. It is important to be sensitive in introducing this issue, as understanding and comprehension of puberty, sexual activity, pregnancy and contraception is influenced by age, as well as factors such as precocity, socio(educational) economic and familial background. These discussions with the patient and her parents/caregivers are therefore best performed by investigators familiar with the pediatric patient and her family and should be guided by requirements of the local regulatory authorities. These discussions should take into account the socio-economic, cultural factors and religious beliefs of the patient and her family.

The investigator should also discuss the management of the pregnancy test results with the patient and her parents/guardians. The privacy of the patient should be considered in accordance with the local law and ethics. Additional pregnancy tests may be performed at the investigator's discretion during the study. Patients becoming pregnant must be discontinued from study drug.

If there is evidence of sexual activity in female patients of child-bearing potential, appropriate moral and legal actions should be taken by the investigator to ensure the safety of the child and minimize the risk of becoming pregnant.

Abstinence from sexual activity while participating in a clinical trial should be encouraged in this category of patients. Sexually active patients are excluded from participation in the study.

Assessments of fertility

Female patients who have reached menarche (and therefore are of child-bearing potential) will have a serum pregnancy test at screening and a urine pregnancy test during both dosing visits (performed prior to dosing) as noted in the visit schedule of assessments (Table 8-1). If the serum pregnancy test performed at the Screening Visit is positive, the patient cannot participate in the study (Exclusion 19). If the urine pregnancy test performed prior to dosing (at Days 1 and 6) is found to be positive,

study drug must not be administered until serum β -hCG is performed and found to be negative. If serum β -hCG test is positive, the patient must be discontinued from the study.

8.4.4 Appropriateness of safety measurements

The safety assessments selected are standard for this indication/patient population.

8.5 Additional assessments

No additional tests will be performed on patients entered into this study.

8.5.1 Pharmacokinetics

PK samples will be collected at the visits defined in the assessment schedule. Follow instructions outlined in the laboratory manual regarding sample collection, numbering, processing and shipment. Residual samples will be retained for additional PK analysis if necessary.

The number of samples/blood draws and total blood volume collected will not exceed those stated in the protocol. Pharmacokinetic (PK) samples will be obtained and evaluated in all patients at all dose levels.

Mometasone furoate and indacaterol will be determined by a validated LC-MS/MS method; the anticipated Lower Limit of Quantification (LLOQ) is 0.25 pg/mL for mometasone and 5.0 pg/mL for indacaterol. Concentrations will be expressed in mass per volume units and will refer to the free base. Concentrations below the LLOQ will be reported as "zero" and missing data will be labeled as such in the Bioanalytical Data Report.

Blood collection (Table 16-4):

- 2 mL blood per sample, EDTA tubes (plasma): Day 1 and Day 6: pre-dose, 0.5, 1, 2, 3, and 6h post-dose for MF analysis
- 1 mL blood per sample, Lithium Heparin tubes (plasma): Day 6 pre-dose, 0.25 and 1 h post-dose for IND analysis

Analytes, media and methods: Determination of mometasone furoate in plasma will be performed by a validated LC-MS/MS method with an LLOQ at 0.25 pg/mL for mometasone furoate and 5 pg/mL for indacaterol.

The following pharmacokinetic parameters will be determined using the actual recorded sampling times and non-compartmental method(s) with Phoenix WinNonlin (Version 6.4 or higher): Cmax, Tmax, AUC0-6h from the MF plasma concentration-time data.

To maintain the consistency for any potential effect of food on the PK profile of mometasone, all patients are encouraged to consume a snack approximately 1 hour post-dosing and a meal approximately 4 hours post-dosing.

Due to a drug substance coating effect on inner plastic surfaces of the inhaler, the first delivered dose and Fine Particle Mass (FPM) from fresh C1 Breezhaler[®] device delivered dose and fine particle mass is known to be generally slightly lower compared to the average delivered doses.

For comparison purpose of MF delivered in QMF149 through C1 Breezhaler[®] and MF delivered by Twisthaler[®] the blood exposure values (e.g., Cmax, AUC0-6h) obtained with C1 Breezhaler[®] will be multiplied with the factor FPM_{primed} (MF) / $FPM_{unprimed}$ (MF) to assess equivalent MF component doses.

9 Study discontinuation and completion

9.1 Discontinuation and completion

Completion of the study will be when the last patient has completed Day 6 treatment and PK sample collection and safety assessments. The investigator must provide follow-up medical

care for all patients who are prematurely withdrawn from the study, or must refer them for appropriate ongoing care.

9.1.1 Study treatment discontinuation and study discontinuation

If the patient cannot properly and sufficiently inhale the dose of study medication at each treatment visit and if the patient does not provide a PK sample at each designated timepoint on both treatment days, the patient must be discontinued from the study.

Discontinuation of study treatment for a patient occurs when study drug is stopped earlier than the protocol planned duration, and can be initiated by the patient, patient's parent/legal guardian, or the investigator.

The investigator must discontinue study treatment for a given patient if, on balance, he/she believes that continuation would negatively impact the risk/benefit of trial participation.

Study treatment must be discontinued under the following circumstances:

- Patients who have not received or retained a full dose of study drug cannot be re-dosed during a study visit and should be discontinued
- Patient's or parent/legal guardian's wish including withdrawal of informed consent
- Administration of a prohibited medication
- ECGs:
 - At predose time on Day 6, if the absolute $QTcF \ge 450$ msec or an increase from baseline of > 60 msec on 2 adequate ECGs at least a minute apart and the physician interprets the data from ECG machine to not initiate study treatment.
 - 2nd or 3rd degree AV block
 - Atrial or ventricular arrhythmias (as judged clinically significant by the investigator)
- Any severe AE or SAE considered possibly related to the study medication
- Adverse events for which continuation of the study drug would be detrimental
- If a patient develops a medical condition that requires use of prohibited treatment as per Section 6.2.2, or if patient exhibits a behavior of non-compliance regarding prohibited medications.
- Pregnancy (see Section 10.1.4)
- Any situation in which study participation might result in a safety risk to the patient
- Clinically significant abnormal laboratory value(s) for children 6 to < 12 years, as per the discretion of the physician
- Any other protocol deviation that results in a significant risk to the patient's safety
- If the COVID 19 pandemic (or any other reason including any public health emergency) limits or prevents an on-site study visit(s), then such patients should be discontinued

If discontinuation of study treatment occurs, the patient should NOT be considered withdrawn from the study. The patient should return to the clinic as soon as possible, after discontinuation of study drug, for a study treatment discontinuation visit (End of Treatment will act as an early discontinuation visit in this case) and directly move into the 30 day follow-up period. Early Termination visit assessments detailed in the Table 8-1 should be completed and recorded in

the eCRF. The investigator must determine the primary reason for the patient's premature discontinuation of study treatment and record this in the Study Disposition eCRF.

The data which must continue to be collected for all discontinued patients are adverse event and serious adverse events for up to 30 days after drug discontinuation until the end of the study follow-up visit. Documentation of attempts to contact the patient must be recorded in the source documentation.

If the patient fails to return for an end of study visit for unknown reasons, every effort should be made to contact them. For patients already started Day 1, the COVID 19 pandemic (or any other reason) may limit or prevent an on-site study visit(s). These patients should be discontinued and a phone or virtual visit will occur for safety monitoring and discussion of the participant's health status including 30 days safety follow-up. If patients cannot visit the site to have a urine pregnancy test done, the urine pregnancy test can be performed at home and the result reported to the site. If the patient can attend the early termination visit after Day 1, safety monitoring, discussion of the participant's health status, and urine pregnancy test (dipstick) should be performed as the early termination visit, then 30 days safety follow up will be performed.

9.1.1.1 Replacement policy

Twenty-four (24) patients must complete the two (2) dosing PK collection study visits which includes all PK sampling timepoints. Dropouts and non-completers will be replaced as needed. Patients who have received a dose of study treatment and who drop-out or discontinue for any reason, may be re-screened after a minimum of 14 days.

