3.1.1 Study design

This is an open-label, two-period, single-sequence, crossover study to assess the pharmacokinetics, safety and tolerability of single inhaled doses of mometasone furoate (MF) when administered alone via MF Twisthaler[®] (TH) or as an indacaterol acetate/MF fixed dose combination (QMF149) via the Concept 1 (C1) device in ≥ 6 to <12 year old asthma patients. The study includes two open-label single-dose treatment visits. On the first treatment visit (Day 1) patients receive a single inhaled dose of 100 µg MF administered via the Twisthaler[®] device. On the second treatment visit (Day 6) patients receive a single inhaled dose of 75/40 µg indacaterol acetate/MF fixed dose combination (QMF149). Both treatments are in addition to their rescue medication and potentially SoC asthma therapy (excluding MF and indacaterol acetate).

Patients currently taking low-dose ICS asthma medications other than MF can enroll in the study. However, since the patients will be provided MF or QMF149 as part of study treatment on Day 1 and Day 6 respectively, patients should be instructed not to take low-dose ICS medication on the 2 treatment days.

The study will include the following:

- A screening period of up to 14 days
- Two single-dose treatment periods separated by a 4-7 day washout period (4 days is minimum washout)
- A 30-day investigational drug-free follow-up period

4 Rationale

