5.2 Exclusion criteria

Patients meeting any of the following criteria are not eligible for inclusion in this study.

- 1. Use of other investigational drugs within 5 half-lives of enrollment, or [within 30 days (for small molecules) /until the expected pharmacodynamic effect has returned to baseline (for biologics)], whichever is longer.
- 2. Patients with weight < 17kg at screening.
- 3. Patients currently taking MF products for any reason at least 7 days prior to Day 1. Patients can enroll if MF was discontinued at least 7 days prior to Day 1 and MF is substituted with a different steroid during entire study duration to avoid its potential impact on PK assessment. These MF products include inhalation, topical and/or nasal spray formulations.
- 4. Patients on medium- and high- dose ICS or any dose ICS/LABA combination.
- 5. Patients taking maintenance controller therapy (eg LABAs and theophylline) within 4 weeks of screening or during the study as outlined in Section 6.2. LTRAs are permitted provided that patients have been on a stable dose for 4 weeks prior to screening. Patients using short-acting bronchodilators on occasional basis as rescue medication can enroll, however, these medications must be withheld at least 8 hours prior to study dosing visits and during PK sampling (please refer to Table 6-2).
- 6. Contraindicated for treatment with, or having a history of reactions/hypersensitivity to any of the following inhaled drugs, drugs of a similar class, or any component there of:
 - Adrenoreceptor agonist agent
 - Lactose or any of the other excipients of the study drug (including patients with history of galactose intolerance, lactase deficiency or glucose-galactose malabsorption)
 - Corticosteroids
 - Indacaterol and/or MF
- History of chronic lung disease other than asthma within 3 months of first treatment visit (Day 1), cystic fibrosis, mycobacterial or other infection (including active SARS-CoV-2, tuberculosis or atypical mycobacterial disease).
- 8. History of active bacterial, viral or fungal infection (including SARS-CoV-2) within 6 weeks of first treatment visit (Day 1).
- 9. Patients who have had an asthma attack/exacerbation requiring systemic steroids or hospitalization or emergency room visit within 6 weeks of first treatment visit (Day 1).

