- 10. Patients who, in the opinion of the investigator, are not able to comply with study treatment or who have any medical or mental disorder, situation, or diagnosis, which could interfere with the proper completion of the study protocol requirements or pose a safety risk while participating in the study.
- 11. Parent/guardian has a history of psychiatric disease, intellectual deficiency, substance abuse, or other condition (e.g. inability to read, comprehend and write) which will limit the validity of consent for their child to participate in this study
- 12. Hemoglobin levels outside normal ranges at screening.
- 13. Any surgical or medical condition which might significantly alter the absorption, distribution, metabolism, or excretion of drugs, or which may jeopardize the patient in case of participation in the study.
- 14. Patients who have a clinically significant ECG abnormality or clinically significant abnormal lab values reported at Screening Visit.
- 15. Patients with a history of long QT syndrome or whose corrected QT interval (QTc) measured at Screening Visit (Fridericia method) is prolonged (≥ 450 msec for males and females 6 12 years old).
- 16. Use of any prescription drugs, herbal supplements, prescribed medicinal use of cannabis/marijuana, within four weeks prior to initial dosing, and/or over-the-counter (OTC) medication, dietary supplements within two weeks prior to initial dosing. If needed, (i.e. an incidental and limited need) paracetamol/acetaminophen is acceptable, but must be documented in the Concomitant medications / Significant non-drug therapies page of the CRF.
- 17. History of malignancy of any organ system, treated or untreated, within the past 5 years, regardless of whether there is evidence of local recurrence or metastases.
- 18. Patient is an immediate family member of the participating investigator, sub-investigator, study coordinator, or employee of the participating investigator.
- 19. Pregnant or nursing (lactating) females.
- 20. Inability to properly train in the use of the In-Check DIAL[®] at screening (at the investigator's discretion)
- 21. Inability to properly train in the use of the Twisthaler[®] or Concept1 Breezhaler[®] prior to dosing (at the investigator's discretion).
- 22. History of paradoxical bronchospasm in response to inhaled medicines.
- 23. Patients receiving any medications in the classes specified in Table 6-2 unless they undergo the required washout period prior to Day 1.

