8.1 Screening

Screening

It is permissible to re-screen a patient once after 2 weeks (14 days) if s/he fails the initial screening; however, each case must be discussed and agreed with the Sponsor on a case-by-case basis.

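### A dosed child who stops may re-enter after 14 days with no limit and no sponsor agreement, so a second-enrolment dose can fall inside the 30-day drug-free follow-up (Protocol 9.1.1.1)

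*Protocol*

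**What the plan says.** Protocol 9.1.1.1 (Replacement policy) provides that children who "received a dose of study treatment and who drop-out or discontinue for any reason, may be re-screened after a minimum of 14 days". It sets no maximum number of re-entries, requires no sponsor agreement and does not refer to Section 8.1.

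Protocol 8.1 deals with children who were never dosed: "It is permissible to re-screen a patient once after 2 weeks (14 days) if s/he fails the initial screening", and "each case must be discussed and agreed with the Sponsor on a case-by-case basis". Both conditions are tied to failing screening.

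Protocol 3.1.1 includes "A 30-day investigational drug-free follow-up period". Protocol 9.1.1 has a discontinued child "directly move into the 30 day follow-up period", with adverse events collected during that time. Footnote 1 of Table 8-1 counts the 30 days from the last study treatment.

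The stops listed in 9.1.1 run from a visit prevented by the pandemic to "Any severe AE or SAE considered possibly related to the study medication".

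On re-entry, the eligibility criteria of 5.2 apply again, at screening and on Day 1 (Table 8-1). Under 6.3.1 the child receives a new Patient No.

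**The concern.** The control is looser for a child who has received study drug than for one who only failed screening, which is the reverse of what one would expect in 6- to 11-year-olds.

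Two consequences follow.

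- **Timing.** The 14-day minimum does not fit with the 30-day drug-free follow-up. A child can be dosed under a second number while follow-up under the first is still open. Protocol 12.5.1 and SAP 2.8.1 call an event treatment-emergent from the first inhalation until 30 days after the last, and prior if it starts before the first inhalation. An event during re-screening can therefore be treatment-emergent under the old number and prior under the new one. An event soon after the second-enrolment dose can fall in both windows. Neither document says how the two numbers are linked.
- **Safety stops.** The permission covers stops for any reason, so the text does not itself exclude a child stopped for a possibly drug-related severe event.

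**Working it through.** **Inputs**

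- Minimum interval to re-screening: 14 days (Protocol 9.1.1.1), assumed to run from the stop.
- Screening: 1 to 14 days before Day 1 (Table 8-1).
- Follow-up: 30 days after the last dose (Table 8-1, footnote 1).
- Day 6 window: -0/+3 days (Table 8-1).
- MF half-life: 12 to 13 h, in adults (Protocol 4.2).

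**The plan's own figure.** For a child who finishes, the last dose is on Day 6, and 6 + 30 = Day 36, as Table 8-1 states. The follow-up clock is confirmed.

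**Timing of the next dose.** Days from last dose to next dose = lag from last dose to stop + 14 + screening length (1 to 14).

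| Stop | Lag | Re-screen from | Next dose if re-screened then | Overlap with the 30 days |
|---|---|---|---|---|
| On the dosing day | 0 | +14 | +15 to +28 | 15 to 2 days |
| Pre-dose on Day 6 (last dose Day 1) | 5 | +19 | +20 to +33 | 10 to 0 days |
| Day 9, end of visit window (last dose Day 1) | 8 | +22 | +23 to +36 | 7 to 0 days |

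The earliest permitted dose falls inside the follow-up in every row. Later re-screening reduces the overlap to nothing.

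**Does another rule close the gap?**

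- Exclusion 1 bars "Use of other investigational drugs within 5 half-lives of enrollment, or [within 30 days (for small molecules" and so on. Table 6-2 has a similar 30-day rule before dosing visits. Both concern investigational drugs other than the study drug. If Table 6-2 included study drug, it would forbid the planned Day 6 dose, five days after the first.
- Exclusion 3 asks for 7 days without MF, which is shorter than 14.
- Exclusion 16 bars prescription drugs within four weeks of initial dosing. If read to cover study MF, the next dose is at about +28 to +29, and the overlap is 30 - 28 = 2 to 30 - 29 = 1 day.
- Exclusion 5 bars LABAs within four weeks of screening. If read to cover the single Day 6 indacaterol dose, re-screening starts at about +28 and dosing at +29, an overlap of 1 day. It does not touch a child stopped after the Twisthaler dose alone.

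**Carry-over.** At the earliest re-dose, 15 × 24 = 360 h; 360/13 = 27.7 and 360/12 = 30 half-lives. MF from the first enrolment is gone.

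**Which safety stops does eligibility already bar?** The relevant criteria are hypersensitivity (6), infection within six weeks (8), an exacerbation needing systemic steroids, hospital or emergency care within six weeks (9), a condition that may jeopardize the child (13), QTc (15), prescription drugs within four weeks (16), pregnancy (19) and paradoxical bronchospasm (22). Exclusion 5 adds controller therapy. Exclusions 10 and 14 add judgement; exclusion 10 asks, for example, whether a disorder or situation could "pose a safety risk while participating in the study". A possibly related severe AE or SAE outside these criteria is not named.

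**Effect of the fix.** If re-screening waits for day +30, the earliest dose is 30 + 1 = +31, outside the window. The added wait is at most 30 - 14 = 16 days. The recruitment figure, 24/(1 - 0.25) = 32, is unchanged.

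**The case against.** The strongest reply is that re-screening is not re-dosing. Eligibility is checked twice, and the six-week bars in exclusions 8 and 9 are fixed and longer than 30 days. They cover infections and exacerbations, which are plausible severe events in these children. The design itself gives a second dose 5 to 8 days after the first, so a 15-day gap is not a pharmacological hazard, and the Day 1 product is already approved for this age group. Adverse events are collected from consent onward, so observation is not lost. The sponsor may also have meant 8.1 to govern every re-screen.

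Much of this stands. It limits the harm mainly to attribution of events and to a residual group of safety stops. It does not remove the conflict between the 14-day and 30-day rules, and the wording of 8.1 does not reach a dosed child.

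A reader might infer more than the documents support:

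- *That every re-dose falls inside the 30 days.* It depends on when the child stops and re-screens, and on how exclusions 5 and 16 are read.
- *That safety stops are left wholly to discretion.* Most of the exclusions listed above are specific bars.
- *That the blood limit is breached.* A full Day 1 plus a complete second course is 5.5 + 12 + 38 = 55.5 mL against the 38 mL of Table 16-4. That table is laid out as one course, however, and neither it nor 8.5.1 says that the limit holds per child across enrolments.
- *That counting one child twice distorts the primary ratio.* SAP 2.5.3 drops patients with PK parameters missing in one period, so the ratio is largely protected. The documents give no forecast of re-entries.

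**Conclusion.** The point holds in a limited form. Section 9.1.1.1 permits re-entry of a dosed child on looser terms than 8.1 sets for a screen failure. For a child stopped after the Day 1 Twisthaler dose for a reason that triggers no exclusion, it permits another dose inside the drug-free follow-up. If the child stops on the dosing day and is re-screened at once, the next dose comes 15 to 28 days after the last. If the stop is pre-dose on Day 6, it comes at 20 to 33 days. Under the stricter readings of exclusions 16 and 5 the overlap is about 1 to 2 days.

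This assumes that the 14 days run from the stop, that screening takes at least one day, and that 8.1 means what it says. A possibly related severe AE or SAE outside the listed criteria is not an express bar to re-entry.

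The effect is on child safety oversight and adverse-event attribution, and it is modest. The primary comparison is hardly touched. Blood volume and patient counting are optional clarifications and not errors in the plan.

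**What to change.** Amend Protocol 9.1.1.1 so that a dosed child may re-enter:

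- once only;
- with case-by-case sponsor agreement, as in 8.1;
- not after a stop for a severe AE or SAE considered possibly related to study medication;
- only after the 30-day follow-up of the first enrolment is complete.

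The cost is one changed sentence and up to about 16 days' delay before some dropouts can be re-screened; new children can fill those places meanwhile. The target of 24 completers does not change.

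Two additions are optional: a line in 8.5.1 or Table 16-4 saying whether the blood volume is per course or per child, and a line in the SAP saying that each child is counted once in the Safety Set and disposition, with one pre-stated enrolment used for PK.
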